6.1.5.7 Assessment of Causality

The investigator's assessment of an AE's relationship to the investigational product is part of the documentation process, but it is not a factor in determining what is or is not reported in the study. If there is any doubt as to whether a clinical observation is an AE, the event should be reported.

The relationship or association of the investigational product in causing or contributing to the AE will be characterized using the following classification and criteria:

Unrelated: This relationship suggests that there is no association between the investigational product and the reported event.

Possible: This relationship suggests that treatment with the investigational product caused or contributed to the AE, i.e., the event follows a reasonable temporal sequence from the time of drug administration or follows a known response pattern to the investigational product but could also have been produced by other factors.

Probable: This relationship suggests that a reasonable temporal sequence of the event with drug administration exists and, based upon the known pharmacological action of the drug, known or previously reported adverse reactions to the drug or class of drugs, or judgment based on the investigator's clinical experience, the association of the event with the investigational product seems likely. The event disappears or decreases on cessation or reduction of the dose of investigational product.

Definite: This relationship suggests that a definite causal relationship exists between drug administration and the AE, and other conditions (concurrent illness, progression/expression of disease state, or concurrent medication reaction) do not appear to explain the event. The event reappears or worsens if the investigational product is re-administered.

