### **3.8 Evaluation of Treatment Safety**

#### **3.8.1 Adverse Events**

An AE is defined as any untoward medical occurrence in a patient enrolled into this study regardless of its causal relationship to the investigational product. The patient's legal representative (parent[s]/caregiver[s]) will be instructed to contact the investigator at any time if any symptoms develop.

A TEAE is defined as any event not present before exposure to the investigational product or any event already present that worsens in either intensity or frequency after exposure to the investigational product.

All AEs will be reported or observed during the study will be recorded on the AE form in the eCRF. The AE and SAE reporting period begins after administration of study drug through the follow up visit. The Investigator will follow-up on all AEs observed or reported by the subject up to the end of the reporting period unless the event stabilizes and follow-up is no longer necessary. The Investigator will follow-up on SAEs until they are considered resolved or the outcome is known.

The following details will be collected for AEs: description of the AE, onset date/time, action taken with study drug (dose not changed, drug interrupted, drug withdrawn, dose increased, not applicable, or unknown), date/time of resolution, any additional treatment given, outcome

(recovered/resolved, not recovered/not resolved, recovered/resolved with sequelae, recovering/resolving, fatal or unknown), severity (mild, moderate, severe), seriousness (yes, no), relationship to study drug (unrelated, possibly, probably, definitely related or unknown), and whether the AE causes early termination of the subject.

The severity of AEs will be categorized as follows:

- Mild: These events require minimal or no treatment and do not interfere with the patient's daily activities.
- Moderate: An AE that is sufficiently discomforting to interfere with normal activities.
- Severe: These events interrupt a patient's usual daily activity and may require systemic drug therapy or other treatment. Severe events are usually incapacitating.

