### 7.2 Handling of Dropouts or Missing Data

Missing data will not be imputed.

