## 7.12 Analysis of Safety Data

### 7.12.1 Adverse Events

All AEs will be coded to SOC and PT using Medical Dictionary for Regulatory Activities (Version 22.0 or later) and presented by subject in data listings.

A treatment-emergent adverse event (TEAE) is defined as any AE that began or worsened following the start of dosing of Treatment Period 1, Day 1 to Follow-Up.

A treatment-related AE is defined as any TEAE that is assessed by the Investigator as possibly, probably or definitely related to study drug.

Adverse event analyses will be conducted using the Safety Population.

The overall incidence of TEAEs (number and percentage of subjects) as well as the number of events will be summarized for mild TEAEs, moderate TEAEs, severe TEAEs, TEAEs assessed as at least possibly related, SAEs, TEAEs leading to study or drug discontinuation, SAEs related to study drug, life-threatening SAEs and SAEs resulting in death. All AE reports will also include the action taken as a result of the AE such as dose not changed, drug interrupted, drug withdrawn, dose increased, not applicable, or unknown.

The following TEAEs summaries will be presented (where applicable the number of patients (%)) and number of events will be summarized) by SOC and PT for overall treatment group:

- TEAEs
- Treatment-related TEAEs
- TEAEs leading to investigational product discontinuation
- Treatment-related TEAEs leading to investigational product discontinuation
- Serious TEAEs
- Treatment-related serious TEAEs
- TEAEs leading to death
- Treatment-related TEAEs leading to death.

All TEAEs will be summarized by SOC and PT using frequency counts and percentages (i.e., number and percentage of patients with an event); also the number of events will be presented

Tabulations will include an overall incidence of subjects reporting at least one AE, an overall incidence of TEAEs, and incidence within SOC and PT. Each patient may only contribute once (i.e., most severe occurrence) to each of the incidence rates, regardless of the number of occurrences.

For the incidence at the subject level by SOC, PT and relationship to study drug; if a subject experiences more than 1 event within the same SOC and PT, only the most related occurrence (in

descending order of definitely related, probably related, and possibly related) will be included in the incidence.

Listings of AEs, TEAEs, SAEs, TEAEs leading to death and TEAEs leading to study drug discontinuation will also be presented.

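### The SAP collects an 'unknown' causality rating that the protocol lacks, and its definition of treatment-related leaves such events out of every treatment-related AE summary

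*SAP*

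**What the plan says.** Protocol section 6.1.5.7 says that causality "will be characterized using the following classification and criteria" and lists four levels: unrelated, possible, probable and definite. The lowest level is a positive judgement: "Unrelated: This relationship suggests that there is no association between the investigational product and the reported event".

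SAP section 3.8.1 lists the details collected for each event. Among them is "relationship to study drug (unrelated, possibly, probably, definitely related or unknown", which makes five levels.

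SAP section 7.12.1 uses three of these to define relatedness: "A treatment-related AE is defined as any TEAE that is assessed by the Investigator as possibly, probably or definitely related to study drug". The overall AE summary has a line for "TEAEs assessed as at least possibly related". Where a patient has several events under the same term, the most related one is kept, in "descending order of definitely related, probably related, and possibly related".

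On missing data, SAP section 7.2 says "Missing data will not be imputed". SAP section 4 declares no departure from the protocol.

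**The concern.** An event whose relationship cannot be determined is different from one judged to have no association with the drug. The SAP collects the two ratings separately, but its definition of treatment-related excludes both. Doubt about causality can therefore only reduce the related count, never raise it.

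The extra level may also draw events away from 'possible'. The protocol's 'possible' already takes events with plausible timing that might have another cause, so on a four-level form an unsure investigator has a natural place for them, and they count as related. With 'unknown' on offer, the same event can leave the related tables.

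This runs against the SAP's own handling of doubt elsewhere. In section 7.2.1, an event whose start year is missing is treated as treatment-emergent unless its end date falls before the first dose. There uncertainty adds to the safety count; here it subtracts, and no reason is given.

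Safety is the primary objective, and the study has one open-label treatment and no control group. The treatment-related tables will be read as the statement of what the drug caused, so their definition should cover every rating the form allows.

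**Working it through.** The documents give no figure on this point, so there is nothing to reproduce. The check is a comparison of text, followed by an illustration of scale.

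**1. The levels side by side**

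| Place | Levels named |
|---|---|
| Protocol 6.1.5.7 | unrelated, possible, probable, definite |
| SAP 3.8.1, data collected | the same four, plus unknown |
| SAP 7.12.1, treatment-related definition | possible, probable, definite |
| SAP 7.12.1, overall summary | possible or higher |
| SAP 7.12.1, most-related rule | definite, probable, possible |

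'Unknown' appears once, at collection, and in none of the analysis rules.

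**2. What happens to a TEAE rated 'unknown'**

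- It fails the treatment-related definition. It is therefore absent from Tables 14.3.1.3, 14.3.1.5, 14.3.1.7 and 14.3.1.9, which are four of the eight tables by system organ class and preferred term (14.3.1.2 to 14.3.1.9).
- It is not on the scale that the overall summary cuts at 'possible', so it is also absent from the related-TEAE and related-SAE lines there.
- It has no rank in the most-related rule. If a patient has one 'unknown' and one 'unrelated' event under the same term, the rule does not say which is kept.
- It remains in the all-causality tables (all, serious, leading to discontinuation, leading to death) and in the AE listings.

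**3. Whether another rule repairs this**

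SAP 7.2 excludes imputation. The exceptions in 7.2.1 and 7.2.2 deal only with dates for adverse events and medications. Nothing assigns 'unknown' to either side.

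**4. Scale**

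Inputs: N = 35 treated patients, from Protocol 4.2.3, which closes enrolment once 35 have begun Treatment Period 1. Let R be the number of patients with at least one event rated possible or higher, and U the number with an 'unknown' event but none rated possible or higher. U is an assumption, because the documents give no basis for it.

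- Related incidence as the SAP defines it: R/N.
- Related incidence if 'unknown' counts: (R + U)/N.
- Difference: U/N, whatever R is.

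| U | U/N | If R = 0, incidence with 'unknown' counted (exact 95% CI) |
|---|---|---|
| 0 | 0/35 = 0.0% | 0.0% (0 to 10.0) |
| 1 | 1/35 = 2.9% | 2.9% (0.1 to 14.9) |
| 2 | 2/35 = 5.7% | 5.7% (0.7 to 19.2) |
| 3 | 3/35 = 8.6% | 8.6% (1.8 to 23.1) |

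The intervals are Clopper-Pearson. In a sparse table such as related serious events, a single 'unknown' case decides between 0/35 and 1/35.

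**The case against.** The strongest reply is that little of the safety analysis depends on this. The primary endpoint is the incidence of TEAEs regardless of cause, and no formal testing is planned. A serious or fatal event of unknown relationship would still appear in the all-causality tables and listings. It would also be open to the data safety monitoring board, whose review of serious events, discontinuations and deaths under Protocol 6.4 has no causality filter. All of this stands, and it confines the point to the treatment-related summaries.

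A second reply is that the effect may never arise. Investigators are instructed on four levels only, the eCRF itself is not among the documents, and nothing suggests how often 'unknown' will be chosen. This also stands, and it is why the figures are conditional. It does not remove the gap, because the SAP states that the level will be collected.

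A third reply is that counting 'unknown' as related is a convention that may overstate relatedness, and that neither document requires it. That is fair. The true value lies between R/N and (R + U)/N. As defined, the treatment-related tables show only the lower end and do not display U. Showing the number of unknown events separately answers this.

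A reader might infer that the SAP recodes undetermined events as unrelated. It contains no such instruction and plans no table of unrelated events. The events are lost from the related tables by omission. A reader might also infer that investigator causality is the only attribution available. That is too strong, since SAP 6.1.1 also plans to explore exposure against response and the board reviews the data independently.

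**Conclusion.** The mismatch is certain from the text: five levels are collected, four are defined in the protocol, three count as related, and no rule covers the fifth. The stated definition gives a related count that undetermined causality can only lower, and SAP section 4 does not disclose the added level.

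The effect is limited to the related lines of the overall summary and the four treatment-related tables. Measured against counting 'unknown' as related, it is 2.9 points per affected patient, or 2.9 to 8.6 points for an assumed 1 to 3 of 35 patients with no other related event. It is zero if 'unknown' is never used. The documents do not support a claim that the primary safety result is biased. The point should still be settled, because the correction is cheap and a choice made after the events have been seen would be open to challenge.

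**What to change.** Before database lock, amend the SAP as follows:

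- In 7.12.1, count TEAEs of unknown relationship as treatment-related, and show the number of such events and patients separately so that both readings are visible.
- Apply the same rule to the related lines of the overall summary.
- Complete the most-related ranking as definite, probable, possible, unknown, unrelated.
- Record the added level in section 4 as a difference from Protocol 6.1.5.7.

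Alternatively, if the form can still be changed, remove 'unknown' so that collection matches the protocol's four levels. That is a change to data collection, not just to the SAP, and it may come too late.

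If missing causality is also to count as related, state it as an explicit exception to the no-imputation rule in SAP 7.2, since the two would otherwise conflict.

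The SAP route costs a few sentences and no new data. Its downside is that treatment-related counts may rise slightly.

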### 3.8.2 Clinical Laboratory Assessments

Blood and urine samples will be collected for hematology, coagulation, serum chemistry and urinalysis at the time points on Screening and Day 7, Day 28 and on Day 42.

Hematology: Hematocrit, hemoglobin, mean corpuscular hemoglobin, mean corpuscular hemoglobin concentration, mean corpuscular volume, platelet count, red blood cell count, and total and differential (absolute and percent) leukocyte count

Coagulation International normalized ratio, partial thromboplastin time, and prothrombin time

Serum Chemistry: Albumin, alanine aminotransferase, alkaline phosphatase, amylase, anion gap, aspartate aminotransferase, bicarbonate, bilirubin (total and direct), blood urea nitrogen, calcium, chloride, cholesterol (total, high-density lipoprotein, and low-density lipoprotein), creatine phosphokinase, creatinine, gamma-glutamyltransferase, globulin, glucose, lactate dehydrogenase, magnesium, phosphorus, potassium, sodium, total protein, triglycerides, and uric acid

Urinalysis: Appearance, bilirubin, color, glucose, ketones, leukocyte esterase, microscopy (performed if dipstick is positive; includes bacteria, casts, crystals, epithelial cells, red blood cells, and white blood cells), nitrites, occult blood, pH, protein, specific gravity, turbidity, and urobilinogen

Abnormal clinical laboratory values will be flagged as either high or low (or normal or abnormal) based on the reference ranges for each laboratory parameter. The investigator will determine whether any of the abnormally high or low results are clinically significant or not clinically significant. Clinical significance is defined as any variation in results that has medical relevance and may result in an alteration in medical care (e.g., active observation, diagnostic measures, or therapeutic measures). If a clinically significant change from the screening value is noted, the clinically significant value and reason for clinical significance will be documented on the AE page of the eCRF. The investigator will continue to monitor the patient with additional assessments until the value has reached the reference range, or the value at the Screening Period visit, or until the investigator determines that follow-up is no longer medically necessary.

Liver enzymes/LFTs will be assessed in accordance with the guidelines presented in the US Food and Drug Administration (FDA) Guidance for Industry—Drug-Induced Liver Injury: Premarketing Clinical Evaluation (July 2009).

Urine drug screen assessment will be performed locally at screening time point.

### 3.8.3 Vital Signs, Height, Weight, and Body Mass Index

Vital signs measurements will include blood pressure, temperature (measured rectally), pulse rate, and respiratory rate. Vital signs will be measured at Screening, Treatment Period 1 on Day 1, Day 2 prior to discharge, Day 7, Day 21 and Day 28, Treatment Period 2 on Day 42 and Follow-Up visit on Day 56. Height, weight, and body mass index (BMI) will be measured at each clinic visit..

### 3.8.4 Electrocardiograms

The 12-lead ECG will be measured at following time points: Screening, Treatment Period 1 on Day 7 and 28, and Treatment Period 2 on Day 42.

ECG parameters will include RR interval, PR interval, QRS width, QT interval, and QT interval from Fridericia's formula (QTcF). Subjects with ECG assessments will be interpreted locally and will include comments on whether the tracings are normal or abnormal; rhythm, presence of arrhythmia or conduction defects; morphology, any evidence of myocardial infarction, or ST segment, T Wave, and U Wave abnormalities.

The investigator will determine whether any of the 12-lead ECG results are normal or abnormal, and if abnormal results are clinically significant or not clinically significant. Clinical significance

is defined as any variation in results that has medical relevance and may result in an alteration in medical care (e.g., active observation, diagnostic measures, or therapeutic measures). If a clinically significant change from screening values is noted, the clinically significant value and reason for clinical significance will be documented on the AE page of the patient's eCRF and a pediatric cardiology consultation will be prompted.

### 3.8.5 Physical and Neurological Examinations

Subjects with complete physical and neurological examination will be documented at Screening, Day 1, Day 2 prior to discharge, Day 7, Day 21 and Day 28 of Treatment Period 1, Day 42 of Treatment Period 2 and Follow-Up visit on Day 56.

A complete physical examination will include assessment of skin, head, ears, eyes, nose, throat, neck, thyroid, lungs, heart, cardiovascular, abdomen, lymph nodes, and musculoskeletal system/extremities.

A neurological examination will include mental status evaluation, examination of cranial nerves, motor examination (muscle tone, strength, and reflexes), cerebellar examination (coordination and gait), and sensory examination.

### 3.8.6 Concomitant Medications

Use of all concomitant medications will be recorded in the patient's eCRF. This will include all prescription drugs, herbal products, vitamins, minerals and over-the-counter (OTC) medications. The minimum requirement is that the medication name and the dates of administration are to be recorded. Any changes in concomitant medications will also be recorded in the patient's eCRF. Use of drugs known to be CYP3A4 substrates and whose PK has been shown to be impacted in the presence of a CYP3A4 inhibitor will not be allowed during the Screening Period, Treatment Period 1, and Treatment Period 2; use of drugs known to be CYP3A4 substrates and whose PK has been shown to be impacted in the presence of a CYP3A4 inhibitor will not be allowed until 2 or more days after the investigational product has been discontinued.

Concomitant drugs used for treating epileptic seizures will be allowed during the study (excluding felbamate, cannabinoids, and drugs used for treating epileptic seizures known to be CYP3A4 substrates and whose PK has been shown to be impacted in the presence of a CYP3A4 inhibitor) if the doses remain stable during the Screening Period, Treatment Period 1, and Treatment Period 2 (with the exception that rescue medications used for acute treatment of breakthrough seizures which are not known to be CYP3A4 substrates and whose PK has not been shown to be impacted in the presence of a CYP3A4 inhibitor may be administered at any

time during the study). Changes of dosages of drugs used for treating epileptic seizures are permitted 2 or more days after the investigational product has been discontinued. Ketogenic diet and vagus nerve stimulation therapies will not be allowed during the Screening Period, Treatment Period 1, and Treatment Period 2; ketogenic diet and vagus nerve stimulation therapies will not be allowed until 2 or more days after the investigational product has been discontinued.

Prior/concomitant medications will be assessed throughout the study for all patients. Information recorded will include start and stop dates and times, dose, frequency, route of administration, and indication.

### 3.8.7 Protocol Deviation Reporting

A protocol deviation is defined as any intentional or unintentional change to, or noncompliance with, the approved protocol procedures or requirements. Deviations may result from the action or inaction of the subject or investigator.

The following lists of protocol deviations of data may include the following:

Data deviations (captured in the database):

- The patient does not meet the protocol inclusion or exclusion criteria.
- Failure to comply with dispensing or dosing requirements (eg, dosing not administered within the timeframe specified in the protocol)
- Missed visits
- Test requirements, including vital signs, lab tests, physical assessments, PK blood draws, and medical history not followed – either tests not done, incorrect tests done, or not done within the timeframe specified in the protocol
- Failure to obtain consent prior to beginning the study
- The patient is noncompliant with the protocol, defined as failure to perform any portion of scheduled assessments or procedures

Major deviations leading to exclusion from PK population:

- PK data collected during the affected treatment period will be excluded from the study results.
- Inaccurate dosing on the day of PK sampling.
- Missed blood sample or deviations from blood collection times.

Major deviations leading to exclusion from EAS:

- Patients with missing or incomplete/unreadable Day 28 EEG data.

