6.2 Pharmacokinetic Assessments

6.2.1 Pharmacokinetic Blood and Urine Samples

Blood for the analysis of the investigational product in plasma will be collected on Day 1 (Visit 2) and Day 21 (Visit 4 [\pm 2 days]) at the time points/intervals described in [Table 13-2](#). Collections can be performed at any time during the collection intervals. The PK blood sampling scheme may be modified on a case-by-case so as not to exceed a total blood draw limit of 8 mL/kg over 56 days, to a maximum blood draw of 50 mL. Note that the total blood drawn accounts for both blood draws for PK assessment as well as other assessments (i.e.,

clinical laboratory assessments). Urine sampling for PK assessment will be collected by using a plastic urine collection bag following the morning dosing of investigational product on Day 1 and Day 21 (Visit 4 [\pm 2 days]). Pharmacokinetic blood and urine samples may be used for future exploratory purposes outside of this study.

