7.5 Analysis Sets

The following analysis sets will be used in the statistical analyses.

Safety analysis set: The safety analysis set will include all patients who were treated with at least one dose of the investigational product. The safety analysis set will be used for all safety assessments.

Efficacy analysis set (EAS): The efficacy analysis set will include all patients, without any major protocol deviation affecting the efficacy endpoint analysis, who were treated with the investigational product for at least 26 days and completed the Day 28 (Visit 5 [\pm 2 days]) overnight video-EEG. The EAS will be used for all efficacy assessments.

Pharmacokinetic (PK) analysis set: The PK analysis set will include all patients, without any major protocol deviation affecting the secondary endpoint analysis, who were treated with at least one dose of the investigational product and have at least one measurable PK concentration. The PK analysis set will be used for all PK assessments.

Modified efficacy analysis set (mEAS): To evaluate the influence of COVID-19 on the efficacy results, a modified EAS will be considered which, in addition to the original EAS, includes also those patients with major protocol deviations affecting the efficacy endpoint analysis which can be attributed to COVID-19. The same efficacy analyses as in the EAS will also be performed for the mEAS. If both populations coincide (i.e., there are no major protocol violations attributable to COVID-19 which affect the efficacy endpoint analysis) only the analyses in the EAS will be performed.

Other additional listings due to COVID-19 may be described in the SAP.

The major protocol deviations leading to exclusion from the EAS and PK analysis set will be specified in the SAP and finalized prior to the database lock.

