### **3.5 Study Drug Administration**

Investigational product will be administered at 6 mg/kg, orally twice daily, once in the morning and 12 hours following the morning dose during the first 7 days of Treatment Period 1. Starting from the PM dose on the day of Visit 3, the dose will be escalated and patients will receive the investigational product at a dose of 9 mg/kg orally twice daily. Starting on Day 15, the dose will be escalated again and patients will receive the investigational product at a dose of 15 mg/kg orally twice daily until the end of Treatment Period 1. Each dose of the investigational product will be administered after at least a 2-hour fast. Food can be given 2 hours after dosing.

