**Table 3-2 Steady State Pharmacokinetic Sampling Time Points**

Study Period		
Visit	Study Days	Blood Sampling Time Points a
2 b	1	

• 0.5-1.5 hours post-AM dose

• 4-6 hours post-AM dose

• 8 hours post-AM dose time point and pre-PM dose

4 b	21	

• 0.5-1.5 hours post-AM dose

• 4-6 hours post-AM dose

• 8 hours post-AM dose time point and pre-PM dose

a. The PK blood sampling scheme may be modified on a case-by-case basis so as not to exceed a total blood draw limit of 8 mL/kg over 56 days, to a maximum blood draw of 50 mL. Note that the total blood drawn accounts for both blood draws for PK assessment as well as other assessments (i.e., clinical laboratory assessments).

b. The AM dose should be administered at the clinical site prior to the PK blood sampling on Visit 2 & 4.

Urine sampling for PK assessment will be collected for the morning dosing of investigational product on Day 1 and Day 21 (Visit 4 [ $\pm$  2 days]).

Pharmacokinetic blood and urine samples may be used for future exploratory purposes outside of this study.

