### **7.4 Analysis Populations**

The following populations will be analyzed for overall treatment group (JBPOS0101):

- All Enrolled Population: The Enrolled Population will include all patients who signed informed consent.
- Safety Population: The safety population will include all patients who were treated with at least one dose of the investigational product. The safety population will be used for all safety assessments.
- Efficacy Population (EAS): The efficacy population will include all patients, without any major protocol deviation affecting the efficacy endpoint analysis, who were treated with the investigational product for at least 26 days and completed the Day 28 (Visit 5 [ $\pm$  2 days]) overnight video-EEG. The EAS will be used for all efficacy assessments.
- Modified Efficacy Population (mEAS): To evaluate the influence of COVID-19 on the efficacy results, a modified EAS will be considered which, in addition to EAS population, includes also those patients with major protocol deviations affecting the efficacy endpoint analysis which can be attributed to COVID-19. The same efficacy analyses as for EAS population will also be performed for the mEAS population.
- PK Population: The PK population will include all patients, without any major protocol deviation affecting the secondary endpoint analysis, who were treated with at least one dose of the investigational product and have at least one measurable PK concentration. The PK Population will be used for all PK assessments.

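### As written, SAP 3.8.7 lets one missed or off-time blood sample exclude a child from the PK population, with no threshold and against the data minimum in SAP 7.4

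*SAP*

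**What the plan says.** Protocol 7.5 delegates the list: "The major protocol deviations leading to exclusion from the EAS and PK analysis set will be specified in the SAP". SAP 3.8.7 supplies it. Under its heading for major deviations that exclude from the PK population it has three lines:

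- "PK data collected during the affected treatment period will be excluded from the study results"
- inaccurate dosing on a PK sampling day
- "Missed blood sample or deviations from blood collection times"

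SAP 7.4 and Protocol 7.5 define the PK population as patients with at least one dose and one measurable concentration, "without any major protocol deviation affecting the secondary endpoint analysis".

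SAP Table 3-2 and Protocol Table 13-2 list three draws on Day 1 and three on Day 21. The first two have intervals, 0.5 to 1.5 h and 4 to 6 h after the morning dose, and Protocol 6.2.1 adds: "Collections can be performed at any time during the collection intervals". The third is given as "8 hours post-AM dose time point and pre-PM dose". Under SAP 3.5 the drug is given "once in the morning and 12 hours following the morning dose". Protocol 6.2.1 and the table footnotes also allow the sampling scheme to be changed case by case to respect a blood-volume limit.

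SAP 6.1.1 plans non-linear mixed-effects modelling and gives sparse sampling as the reason.

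**The concern.** The sampling line has no lower limit. It does not say how many samples must be missed, how late a draw must be, or whether a PK parameter must be affected. Taken at its word, a child with five good concentrations and one missed draw leaves the PK population, and all PK assessments are based on that population.

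This conflicts with the rest of the plan. A one-concentration minimum has little purpose if any missed draw excludes. A mixed-effects model with actual times can use incomplete and irregular profiles, so excluding the child for one draw works against the method the SAP chose.

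Two further points are unsettled: how far the treatment-period sentence reaches, and what counts as on time for the third draw. PK is the only secondary objective. Either usable data are discarded, or membership is decided before lock by unwritten judgement.

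**Working it through.** The documents state no expected PK-population size or exclusion rate, so there is no figure to reproduce. The check is a reading of the text followed by an illustration.

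**Scope of the treatment-period sentence.** Treatment Period 1 runs from Day 1 to Day 28, so both PK days fall inside it. If the affected treatment period means Treatment Period 1, all of a child's PK data go. If it means the PK day concerned, the other day's data stay. The SAP does not say which.

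**Third draw.** The evening dose is due 12 h after the morning dose. A 10 h draw is off-time if the line means 8 h, and on time if it means 8 h up to the evening dose.

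**Illustration.** Inputs:

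- 35 dosed (Protocol 7.4, SAP 7.13)
- 6 draws per child, 3 on each of 2 days (Table 3-2), all taken as due
- failure rate f per draw, where failure means missed or off-time; this is assumed, as the documents give none

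Formulas:

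- A. Literal rule, independent failures: 35 × (1−f)^6
- B. On-time concentrations discarded under A: 210 × (1−f) − 210 × (1−f)^6
- C. Literal rule, failures clustered within child (beta-binomial, intraclass correlation ρ = 0.3, also assumed): 35 × the product over i = 0 to 5 of [(1−f)(1−ρ) + iρ] / [(1−ρ) + iρ]
- D. PK-day reading, children keeping at least one intact day: 35 × {1 − [1 − (1−f)^3]^2}

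| f | (1−f)^6 | A: children kept | B: on-time samples discarded | C: children kept, clustered | D: children with an intact day |
|---|---|---|---|---|---|
| 1% | 0.9415 | 33.0 | 10.2 of 207.9 | 33.8 | 35.0 |
| 2% | 0.8858 | 31.0 | 19.8 of 205.8 | 32.7 | 34.9 |
| 5% | 0.7351 | 25.7 | 45.1 of 199.5 | 29.5 | 34.3 |
| 10% | 0.5314 | 18.6 | 77.4 of 189.0 | 24.7 | 32.4 |

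Worked line for f = 5%: 0.95^6 = 0.7351, and × 35 = 25.7. On-time samples discarded are 199.5 − 154.4 = 45.1.

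If the one-concentration minimum alone decided membership, and every on-time draw were measurable, 35 × (1 − f^6) rounds to 35.0 at each of these rates.

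**The case against.** The strongest defence is that the literal reading is not the intended one. The lists in SAP 3.8.7 are introduced as things that may be included. SAP 7.4 counts only major deviations that affect the secondary endpoint, its one-sample minimum points to leniency, and SAP 7.6 has major deviations identified before lock. On that reading the loss may be zero. This stands as a possible reading, but none of these provisions says when a missed or late draw matters.

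The separate Modelling & Simulation Analysis Plan, which is not available here, may handle off-time samples. That could limit the effect on the model, but PK-population membership is set in the SAP. PK is also descriptive here, with no formal testing.

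A reader might infer several stronger points that the documents do not support:

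- *SAP 3.8.7 contradicts itself because its first list also covers PK draws* ("either tests not done, incorrect tests done, or not done within the timeframe specified in the protocol"). That list is headed as deviations captured in the database, which says where they are recorded and not how grave they are. It also contains consent and eligibility failures, so the second list can be a subset of it.
- *The treatment-period sentence sets no limit.* Its scope is unclear; a PK-day reading would limit the loss.
- *The third draw has no window at all.* Its wording can be read as bounded by 8 h and the evening dose. The fault is ambiguity.
- *Excluded concentrations vanish from the report.* Listing 16.2.5.2 is restricted to the PK population, but SAP 7.1 promises listings of all database results, and SAP 7.11 says individual profiles show every assayed concentration. The text is mixed.

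**Conclusion.** The point holds and should be fixed before lock. SAP 3.8.7 is the operative list, and its sampling line has no threshold. Applied as written, it removes a child's valid concentrations for one missed or off-time draw, contrary to the data minimum in SAP 7.4 and the reasoning of SAP 6.1.1.

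The size is uncertain. Possible losses run from none, under the lenient reading, to roughly 16 of 35 children under the literal rule if all six draws fail independently at 10% (35 − 18.6 = 16.4). Every failure rate and the clustering value are assumptions, and the table counts the third line as one draw per PK day. A reader might infer that the PK population will fall below the 26 planned completers. The documents do not support that: they give no failure rate, and they set 26 as a target for study completers, not for the PK population.

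**What to change.** Edit SAP 3.8.7 before database lock:

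1. Remove the missed or off-time sample bullet from the patient-level PK exclusions. State that such a sample does not by itself exclude a patient who otherwise meets SAP 7.4.
2. State that the population PK model uses actual dose and sampling times, or refer to the Modelling & Simulation Analysis Plan if it already says so. On grounds of sample timing, exclude only individual concentrations whose dose or sampling time cannot be established.
3. Leave off-window samples out of by-time-point summaries only. For that purpose, treat the third sample as in window from 8 h after the morning dose until the evening dose.
4. Keep the treatment-period sentence, but move it out of the list of criteria. Reword it so that inaccurate dosing removes the PK data of the affected PK day (Day 1 or Day 21) and not the patient. Deleting it outright would leave the inaccurate-dosing bullet with no limit on its scope.
5. State that draws omitted under the permitted blood-volume modification, or not due after withdrawal, are not major deviations.

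If no patient-level PK exclusion then remains in the list, say so, because Protocol 7.5 sends the reader to the SAP for it. SAP 7.4 and Protocol 7.5 need no change and no new data are required. The cost is a short text edit and a little sample-level data handling.
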